Inking – Specimen or Surface A procedure performed as part of SoC, wherein a specific colour of ink is applied to a specific surface or margin of a tissue specimen for the purposes of orienting tissue blocks during histopathological analysis. Up to six colours may be used to orient the *primary specimen or shaves*.

Index Surgery/ Surgical Procedure The first surgery performed to remove a primary breast cancer.

In vivo Fluorescence assessment / inside surface

Ex vivo

surface

[figure not shown]
Fluorescence

Determination of the FL status of tissue based on FL imaging of tissue that is inside the patient (not yet resected).

The inside surface of cavity shave specimen(s) and the final cavity after FGR can undergo in vivo FL assessment.

Determination of the FL status of tissue based on FL imaging of resected tissue *specimen(s)* after removal from the patient (i.e., outside the patient).

The outside surface of the primary specimen, final margins after SoC and outside surface of cavity shave specimen(s) can undergo ex vivo FL assessment.

Orientation-level

assessment / outside

An endpoint for which *orientation*-based analysis is performed. An *orientation-level* analysis would evaluate each *orientation* as a single data point with a total of at least 5 *orientations* per patient (in cases where an area of skin is removed with the lump, there may be n = 5 data points per patient). *Orientation-level* analysis evaluates efficacy based on the performance characteristics (accuracy) in each anatomical location of the entire surgical cavity.

Patient-level endpoint

endpoint

An endpoint for which patient-based analysis is performed. A *patient-level* analysis evaluates each patient as a single data point.

Surgeon

The surgeon responsible for performing the SoC breast conserving surgery procedure and real-time intraoperative interpretation of the Eagle V1.2 Imaging System data.

carcinoma during breast conserving surgery	SBI-CIP 20-002	Rev: v1.8	A prospective multi-center clinical study evaluating the use of PD G 506 A and the Eagle V1.2 Imaging System for the visualization of carcinoma during breast conserving surgery	Page: 20 of 157
--	-----------------------	--------------	--	-----------------

The individual responsible for performing Eagle V1.2 Imaging System fluorescence imaging of the *primary specimen* and any *SoC cavity shave specimens* prior to opening of the randomization envelope.

Surgeon's Assistant

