The *surgeon's assistant* may be a qualified staff *surgeon*, surgical fellow, resident, nurse, physician's assistant, research manager or research coordinator.

True Positive Orientation (TP₀)

Orientation that is fluorescence positive and histopathology positive.

True Negative Orientation (TN₀)

Orientation that is fluorescence negative and histopathology negative.

False Positive Orientation (FP₀)

Orientation that is fluorescence positive and histopathology negative.

False Negative Orientation (FN₀)

Orientation that is fluorescence negative and histopathology positive.

True Positive Patient

Patient has at least one *TP orientation* without any *FN orientations*

True Negative Patient

Patient has all TN orientations

False Positive Patient

Patient has at least one FP orientation without any FN or TP

orientations

False Negative Patient

Patient has at least one FN orientation

SBI-CIP 20-002	Rev: v1.8	A prospective multi-center clinical study evaluating the use of PD G 506 A and the Eagle V1.2 Imaging System for the visualization of carcinoma during breast conserving surgery	Page: 21 of 157
-----------------------	--------------	--	-----------------

6. Introduction

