	Patient-level specificity of PD G 506 A-induced fluorescence (following SoC BCS) to determine the presence or absence of residual cancer in the surgical cavity at the end of FGR as compared to the final margin histopathology.	P(2.6) Specificity = TN Patient TN Patient + FP Patient	x 100%	Patient-level specificity to identify residual carcinoma after FGR is complete.

SBI-CIP 20-002 Rev: v1.8 A prospective multi-center clinical study evaluating the use of PD G 506 A and the Eagle V1.2 Imaging System for the visualization of carcinoma during breast conserving surgery	Page: 33 of 157
---	-----------------

Secondary Objectives	Parameter Description	Parameter Formula		Abbreviated Description
7. To characterize the diagnostic performance of PD G 506 A to identify malignant breast tissue (Arm 2 only).	Patient-level Positive Predictive Value (PPV) of PD G 506 A-induced fluorescence (following SoC BCS) to determine the presence or absence of residual cancer in the surgical cavity at the initial fluorescence assessment at end of SoC as compared to the margin histopathology.	P(2.7) PPV = TP Patient TP Patient + FP Patient	x 100%	Patient-level PPV to identify residual carcinoma at the initial fluorescence assessment at end of SoC.
	Patient-level Negative Predictive Value (NPV) of PD G 506 A-induced fluorescence (following SoC BCS) to determine the presence or absence of residual cancer in the surgical cavity at the initial fluorescence assessment at end of SoC as compared to the margin histopathology.	P(2.7) NPV = TN Patient TN Patient + FN Patient	x 100%	Patient-level NPV to identify residual carcinoma at the initial fluorescence assessment at end of SoC.
8. To characterize the	Patient-level diagnostic performance characteristics of sensitivity,	P(2.8) Sensitivity = TP Patient	X	Patient-level diagnostic performance of PD G 506 A
diagnostic performance of PD	specificity, PPV and NPV to determine	TP Patient + FN Patient	100%	to detect cancer after SoC
G 506 A to identify malignant breast tissue (Arm 2 only).	the presence or absence of cancer in the surgical cavity after SoC BCS. For this analysis, all orientations	P(2.8) Specificity = TN Patient TN Patient + FP Patient	x 100%	BCS.
	following SoC through the end of FGR are considered in definitions of TP Patient, TN Patient, FP Patient and FN	P(2.8) PPV = TP Patient TP Patient + FP Patient	x 100%	
	Patient.	P(2.8) NPV = TN Patient TN Patient + FN Patient	x 100%	

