SBI-CIP 20-002 Rev: v1.8 A prospective multi-center clinical study evaluating the use of PD G 506 A and the Eagle V1.2 Imaging System for the visualization of carcinoma during breast conserving surgery	Page: 34 of 157
---	-----------------

Secondary Objectives	Parameter Description	Parameter Formula		Abbreviated Description
9 To characterize the diagnostic performance of PD G 506 A to identify malignant breast tissue (Arm 2 only).	Percentage of patients assessed as residual tumor negative at the end of FGR (i.e., the final surgical cavity after FGR is completely FL-negative as are the corresponding final margin surfaces) who had positive margins on histopathology.	P(2.9a) = FN Patient #patients assessed residual tumor negative by FL imaging at the end of surgery(i.e., TN patient + FN patient) P(2.9b) = FN Patient	x100% x100%	Patient-level false negative rate of carcinoma at the end of FGR.
10. To characterize the diagnostic performance of PD G 506 A to identify malignant breast tissue after SoC BCS (Arm 2 only).	Percentage of patients assessed as residual tumor positive by FL imaging at the initial fluorescence assessment at end of SoC (i.e., at least one orientation having a surface that was FL-positive either in the cavity or on the corresponding final shave or specimen margin at the end of SoC) who had negative margins on pathology following SoC and no cancer identified in any FL-guided shave specimen.	All patients imaged (Arm 2) P (2.10a) = # patients with ≥ 1 FL-positive orientation at the end of SoC and all carcinoma-negative final margins after SoC and carcinoma-negative FL- driven cavity shave specimens # patients assessed residual tumor positive by FL imaging at the end of SoC	x100%	Percentage of patients in whom SOC final margins were carcinoma negative and all FL-driven shave specimens were carcinomanegative (patient-level false positive rate).
	in any 1 L-guided shave specimen.	P (2.10b) = # patients with ≥ 1 FL-positive orientation at the end of SoC and all carcinoma-negative final margins after SoC and carcinoma-negative FL- driven cavity shave specimens All patients imaged (Arm 2)	x100%	

SBI-CIP 20-002 Rev: v1.8 A prospective multi-center clinical study evaluating the use of PD G 506 A and the Eagle V1.2 Imaging System for the visualization of carcinoma during breast conserving surgery	Page: 35 of 157
---	-----------------

Secondary Objectives	Parameter Description	Parameter Formula		Abbreviated Description

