11. To determine how often FGR with PD G 506 A will result in the removal of any additional carcinoma	Percentage of patients with histopathology-negative margins at the initial fluorescence assessment at the end of SoC who have at least one orientation that was both FL-positive and histopathology-positive.	P(2.11a) = # patients with histopathology-negative final margins after SoC and at least one FGR TP orientation # patients with histopathology-negative final margins after SoC	x100%	Percentage of patients with carcinoma-negative margins after SoC found to have residual tumor following SoC that was identified intraoperatively with combined FL imaging.
	This analysis is only done in those patients who have a FL driven shave obtained as a result of FL-positive orientation identified after SoC. Patients who have cancer anywhere in a FL driven shave obtained as a result of the FL-positive orientation can contribute to the numerator of this endpoint.	P(2.11b) = # patients with histopathology-negative final margins after SoC and at least one FGR TP orientation All patients imaged (Arm 2)	x100%	
12.To characterize the diagnostic performance of PD G 506 A to identify malignant breast tissue after SoC BCS (Arm 2 only).	Percentage of patients with no fluorescence identified at the initial fluorescence assessment at the end of SoC (in either the cavity or on the corresponding final margin surfaces after SoC) in whom all final margins after SoC are histopathologically	P(2.12a) = # patients with only FL-negative orientations after SoC and histopathology negative final margins after SoC (i.e. TN Patient after SoC) # patients with only FL-negative orientations after SoC P(2.12b) =	x100%	
	confirmed to be negative for carcinoma.	# patients with only FL-negative orientations after SoC and histopathology negative final margins after SoC (i.e. TN Patient after SoC) All patients imaged (Arm 2)		
13. To characterize the diagnostic performance of in vivo imaging of PD G 506 A	Patient-level in vivo diagnostic performance of PD G 506 A-induced fluorescence (following SoC BCS) to	$\frac{P(2.13) \text{ Sensitivity} = }{\text{TP Patient } (in \ vivo)}$ $\frac{\text{TP Patient } (in \ vivo) + \text{FN Patient } (in \ vivo)}{\text{TP Patient } (in \ vivo)}$	x100%	Patient-level in vivo diagnostic performance to

SBI-CIP 20-002

Secondary Objectives	Parameter Description	Parameter Formula		Abbreviated Description

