15.3. Definitions of Units of Analysis

The definitions of TP, TN, FP, and FN at the units of analysis of orientation, patient and primary specimen are provided in Table 15.1.

SBI-CIP 20-002 Rev: v1.8 A prospective multi-center clinical study evaluating the use of PD G 506 A and the Eagle V1.2 Imaging System for the visualization of carcinoma during breast conserving surgery	Page: 97 of 157
---	-----------------

Table 15.1: Levels of Analysis and Diagnostic Performance Definitions

Diagnostic Performance	Orientation Level	Patient Level	Primary Specimen Level
Parameter	Analysis	Analysis	
_			Analysis A primary specimen level analysis evaluates each biopsy from the bisected primary specimen (i.e., primary tumor mass) as a single data point. At most, there will be one FL-positive and one FL-negative biopsy per patient included in the analysis.
	An orientation is comprised of two contiguous tissue surfaces that have been separated by a scalpel (or other surgical tool e.g., electrocautery) during tissue resection. The tissue surfaces are from the primary specimen, cavity shave specimens, and the final cavity surface. An orientation is described based on the anatomical location of the contiguous tissues (e.g. S, M, P, L, I, A).		
True Positive	Orientation that is fluorescence positive and histopathology positive.	Patient has at least one TP orientation without any FN orientations	Fluorescence is observed in the primary specimen biopsy that is histopathology-positive for carcinoma
True Negative	FL-negative orientation with final margin for that orientation from cavity shave specimens or primary specimen (if no shaves taken) negative on histopathology	Patient has all TN orientations	No fluorescence is observed in the primary specimen biopsy that is histopathology-negative for carcinoma

SBI-CIP 20-002	Rev: v1.8	A prospective multi-center clinical study evaluating the use of PD G 506 A and the Eagle V1.2 Imaging System for the visualization of carcinoma during breast conserving surgery	Page: 98 of 157
-----------------------	--------------	--	-----------------

Diagnostic Performance Parameter	Orientation Level Analysis	Patient Level Analysis	Primary Specimen Level Analysis

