False Positive	FL-positive orientation with final margin for that orientation from cavity shave specimens or primary specimen (if no shaves taken) negative on histopathology	Patient has at least one FP orientation without any FN or TP orientations	Fluorescence is observed in the primary specimen biopsy that is histopathology-negative for carcinoma
False Negative	FL-negative orientation with final margin for that orientation from cavity shave specimens or primary specimen (if no shaves taken) positive on histopathology	Patient has at least one FN orientation has at least	No fluorescence is observed in the primary specimen biopsy and the biopsy is histopathology- positive for carcinoma

SBI-CIP Rev 20-002 v1.8	A prospective multi-center clinical study evaluating the use of PD G 506 A and the Eagle V1.2 Imaging System for the visualization of carcinoma during breast conserving surgery	Page: 99 of 157
----------------------------	--	-----------------

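### Patient-level PPV and NPV in P(2.7) and P(2.8) are not conditioned on the imaging result, because a False Negative Patient may also have fluorescing orientations

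*Combined protocol and SAP*

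**What the plan says.** Section 5.2 and Table 15.1 (Section 15.3) sort each patient into one of four classes from her orientations, with false negatives taking precedence:

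- FN Patient: "Patient has at least one FN orientation", with no condition on her other orientations.
- TP Patient: "Patient has at least one TP orientation without any FN orientations".
- FP Patient: "Patient has at least one FP orientation without any FN or TP orientations".
- TN Patient: "Patient has all TN orientations".

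Section 5.2 counts each orientation "as a single data point with a total of at least 5 *orientations* per patient", so one patient can easily hold several kinds.

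Section 7.2.2 reuses these classes for predictive values. P(2.7) has "P(2.7) NPV = TN Patient TN Patient + FN Patient" and PPV = TP/(TP+FP), both at the initial fluorescence assessment at the end of SoC. P(2.8) uses the same formulas over all orientations from the end of SoC to the end of FGR. P(2.13) and, in Section 7.3, E.19 repeat them for in vivo and ex vivo imaging at the end of FGR.

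P(2.9a) describes its group as patients with no fluorescence left in the cavity or on the final margins, but writes the denominator as patients "assessed residual tumor negative by FL imaging at the end of surgery(i.e., TN patient + FN patient". P(2.12a) has TN Patient after SoC as its numerator and divides by "patients with only FL-negative orientations after SoC". Section 15.5 names Section 7 as the place for the detailed formulas.

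**The concern.** A predictive value answers a question about a test result: given a fluorescing cavity, or a clear one, how likely is cancer? Its denominator has to be everyone with that result. Giving FN precedence is a sound, location-matched choice for sensitivity, since a patient with any missed margin is not credited as detected. Carried into PPV and NPV, the same precedence puts women whose imaging was positive, and who were shaved because of it, among the test-negatives.

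At stake is whether the reported PPV and NPV mean what their names say. There is also a consistency problem: P(2.7) NPV and P(2.12a) could give two values for the chance of clear margins when nothing fluoresced at the end of SoC.

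**Working it through.** **1. Scale, and the plan's own convention.** The plan states no expected patient-level PPV or NPV to reproduce. Its Arm 2 size does reproduce: with p0 = 1%, p1 = 3%, two-sided 0.05 and 90% power, n = [1.96·√(0.01·0.99) + 1.2816·√(0.03·0.97)]² / 0.02² = 427.7, so 428. Table 6.1, from the earlier study, conditions on the fluorescence result: at the low dose NPV = 22/(22+7) = 75.9% and PPV = 13/(13+4) = 76.5%, each over all samples with that result. The patient-level formulas look the same but do not inherit that property.

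**2. Which patients fall in which class.** A patient can hold any non-empty combination of the four orientation types, which gives 15 patterns.

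| Class | Patterns | With an FL-positive orientation | Histology-positive |
|---|---|---|---|
| FN Patient | 8 | 6 | 8 |
| TP Patient | 4 | 4 | 4 |
| FP Patient | 2 | 2 | 0 |
| TN Patient | 1 | 0 | 0 |

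These are counts of patterns, not frequencies. TP+FN is every histology-positive patient and TN+FP every histology-negative one, so sensitivity and specificity keep valid denominators. TN+FN is not the FL-negative group: only the patterns {FN} and {FN, TN} belong there. TP+FP is not the FL-positive group.

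**3. P(2.7) NPV against P(2.12a).** Both are taken at the end of SoC. Section 15.4.4.1 adds histology from the inside of the first FL-driven shave, but Section 12.4.3 gives no such shave to a patient with no fluorescence, so the TN Patient numerator is the same. Only the denominators differ.

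**4. Size.** Inputs: N = 428 (Section 15.2); sensitivity 70% and specificity 80%, the lower ends of the stated expectations (Section 15.6.2). Assumption: 20% margin-positive, back-calculated as 3%/15% from expected P(1.1) and P(2.1); the documents do not state it. Assumption: a share f of FN Patients also has an FL-positive orientation; the documents give no value.

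Margin-positive 85.6: TP 59.92, FN 25.68. Margin-negative 342.4: TN 273.92, FP 68.48.

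As written: NPV = 273.92/299.60 = 91.4%; PPV = 59.92/128.40 = 46.7%.

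Conditioned on fluorescence, with m = f·25.68 mixed patients:

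- NPV = 273.92/(299.60 − m)
- PPV, all mixed TP+FN = (59.92 + m)/(128.40 + m)
- PPV, all mixed FP+FN = 59.92/(128.40 + m)

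| f | m | NPV | PPV, TP+FN | PPV, FP+FN |
|---|---|---|---|---|
| 0 | 0 | 91.4% | 46.7% | 46.7% |
| 10% | 2.57 | 92.2% | 47.7% | 45.8% |
| 25% | 6.42 | 93.4% | 49.2% | 44.4% |
| 50% | 12.84 | 95.5% | 51.5% | 42.4% |

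Range over prevalence, in whole patients: at 15% (TN 291, FN 19) NPV is 93.9% as written, against 95.4% at f = 25% and 97.0% at f = 50%. At 30% (TN 240, FN 38) it is 86.3%, against 89.6% and 92.7%.

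**5. End-of-FGR endpoints.** Under Section 12.4.3, FGR continues until no red fluorescence remains or no more tissue can be removed. At that point an FN Patient is FL-positive elsewhere only if fluorescence was left unresected. The protocol allows this and has it recorded. P(2.9a), P(2.13) and E.19 are affected only through such patients, so the figures in step 4 do not apply to them.

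**The case against.** The strongest reply is that the plan already holds the figures a surgeon needs. P(2.12a) conditions on no fluorescence at the end of SoC. P(2.10a) conditions on fluorescence and reports the share with no cancer in SoC margins or FL-driven shaves. That stands: a reader might infer that the plan nowhere says what a fluorescing or clear cavity means, and these two endpoints show otherwise. It does not rescue P(2.7) and P(2.8), which carry the names PPV and NPV and can sit beside P(2.12a) with a different value.

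Second, these are non-key secondary or exploratory estimates with Wilson intervals and no hypothesis test, and the NPV error works against the product. With whole-patient counts, the NPV shifts at 10% and 25% overlap lie inside the Wilson interval for 274/300 (87.6% to 94.0%), and every PPV shift shown lies inside that for 60/128 (38.4% to 55.5%). This limits the consequence. It does not make the definition right, because the shift is systematic, and the NPV shift at 50% overlap falls outside its interval.

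Third, in P(2.9a) the description and the main words of the denominator name the right group, and only the gloss is wrong. That is accepted. A reader might infer that the end-of-FGR endpoints are distorted as much as P(2.7). They are not, since the distortion needs unresected fluorescence.

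**Conclusion.** The point holds for P(2.7) and P(2.8). Their PPV and NPV are not conditioned on the imaging result, and nothing elsewhere in the protocol repairs this. NPV is understated whenever any FN Patient also fluoresced: by 0.8, 2.0 or 4.1 points at 10%, 25% or 50% overlap under the assumptions above, and by at most 8.6 points if all did. With no overlap the two versions agree. P(2.8) is the more exposed, because a patient with a TP orientation after SoC and an FN orientation later in FGR also lands among its test-negatives.

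A reader might infer that PPV is understated too. The documents do not fix the sign: it rises if the mixed patients are mainly TP+FN and falls if they are mainly FP+FN.

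The gloss in P(2.9a) contradicts that endpoint's own description, with an effect limited to patients with unresected fluorescence. Sensitivity, specificity, P(1.1) and P(2.1) to P(2.3) are untouched. This should be corrected before the data are analysed, but it does not threaten the trial's main conclusion.

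**What to change.** Keep the four patient classes for sensitivity and specificity. Define patient-level fluorescence status at each time point: positive if any orientation is FL-positive, otherwise negative. Then:

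- **NPV:** compute it among patients with only FL-negative orientations. For P(2.7) this equals P(2.12a), so cross-reference it. For P(2.8) the pooled group reduces to the same patients, since no fluorescence at the end of SoC means no FL-driven shave; do not report it as a separate result.
- **PPV:** patients with at least one TP orientation, divided by patients with at least one FL-positive orientation. Tabulate mixed TP+FN and FP+FN patients separately.
- **P(2.9a):** delete the gloss and restrict numerator and denominator to patients with every orientation FL-negative at the end of FGR. P(2.9b) shares the FN count and should follow.
- **P(2.13) and E.19:** apply the same conditioning, using in vivo and ex vivo status respectively.

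The cost is wording in the endpoint tables and SAP. No new data are needed, because Section 12.4.3 already records fluorescence status for every surface. The drawback is that predictive values will no longer come from the same four-cell table as sensitivity and specificity, which the report should say.

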Final Margin(s)	Final margin is comprised of the outside surface of the last resected tissue(s) for each anatomical surface and the final cavity at that margin. Final margins are evaluated to determine whether the patient has positive or negative margins based on postoperative clinical pathology assessment. For each patient, final margins after SoC and final margins after FGR will be evaluated histopathologically. If there are no FL-driven cavity shave specimens collected in a patient randomized to receive FGR , then the final margins after FGR are equivalent to the final margins after SoC .			
Positive Margins	Surgical Oncology as follows:			
		Surface histo	pathology status Positive	Negative
True Positive Orientation	Surface fluorescence	Positive	True positive (TP)	False positive (FP)
	status	Negative	False Negative (FN)	True Negative (TN)
and True Negative Orientation	a. A TP orientation contains at least 1 True Positive surface. b. A FN orientation contains at least 1 False Negative surface and no True Positive surface. c. A FP orientation contains at least 1 False Positive surface and no True Positive or False Negative surfaces. d. A TN orientation contains only True Negative surfaces.			

SBI-CIP	Rev: v1.8	A prospective multi-center clinical study evaluating the use of PD G 506 A and the Eagle V1.2 Imaging System for the visualization of	Page: 18 of 157
20-002	V1.0	carcinoma during breast conserving surgery	

Re-excisions

A re-excision is defined as a surgical procedure performed in the ipsilateral breast following the primary lumpectomy because of positive margins found from the initial lumpectomy procedure. The re-excision procedure can be a separate surgical procedure to excise further breast tissue or a mastectomy.

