to identify malignant breast tissue (Arm 2 only).	determine the presence or absence of residual cancer in the surgical cavity at the end of FGR as compared to the final margin histopathology.	P(2.13) Specificity = TN Patient TN Patient + FP Patient	x100%	identify residual carcinoma after FGR is complete.
	Only FL-positive orientation-in vivo and FL-negative orientation-in vivo orientations are included in the patient- level diagnostic performance	$\frac{P(2.13) \text{ PPV} =}{\text{TP Patient } (in \ vivo)}$ $\frac{\text{TP Patient } (in \ vivo) + \text{FP Patient } (in \ vivo)}{\text{TP Patient } (in \ vivo)}$	x100%	
	definitions for this analysis. FL-assessment of in vivo tissue in the final cavity will be compared to histopathological status of final margins of the ex vivo tissue specimens.	$\frac{P(2.13) \text{ NPV} = \frac{\text{TN Patient } (in \ vivo)}{\text{TN Patient } (in \ vivo) + \text{FN Patient } (in \ vivo)}$	x100%	
14. To determine the frequency with which fluorescence is found only on one of the opposing surfaces in an orientation.	Percentage of orientations where in vivo FL imaging disagrees with ex vivo FL imaging (e.g., FL-negative cavity surface but FL-positive corresponding shave or specimen margin surface, or vice versa). FL imaging at all points during the surgery (not just at the end) are used for this endpoint.	P(2.14) = # orientations where FL status of Orientation-in vivo is discordant with FL status of Orientation-ex vivo All Orientations	x100%	Percentage of orientations with discordant FL status.
15. To characterize the impact of FGR on the rate of 2 nd surgery within 1 year	Percentage of patients receiving a 2 nd surgery on the ipsilateral breast within 1 year of index BCS to remove	P(2.15a) Arm 1 only =	x100%	Patient-level re-operation rate due to suspected residual disease.

SBI-CIP 20-002 Rev: v1.8 A prospective multi-center clinical study evaluating the use of PD G 506 A and the Eagle V1.2 Imaging System for the visualization of carcinoma during breast conserving surgery	Page: 37 of 157
---	-----------------

Secondary Objectives	Parameter Description	Parameter Formula		Abbreviated Description

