following index BCS (Arm 1 and Arm 2).	suspected residual disease (patient-level analysis; Arm 1 and Arm 2).	# of patients in Arm 1 that underwent a 2 nd surgery on the ipsilateral breast within 1 year of index BCS # of patients in Arm 1 # of patients in Arm 2 that underwent a 2 nd surgery on the ipsilateral breast within 1 year of index BCS # of patients in Arm 2	x100%	
16. To characterize the impact of FGR on the rate of 2 nd surgery shortly after index BCS (Arm 1 and Arm 2).	Percentage of patients receiving an early 2 nd surgery (planned or actual) on the ipsilateral breast related to positive final margins prior to radiation or medical management (patient-level analysis; Arm 1 and Arm 2).	# of patients in Arm 1 that underwent or are scheduled to undergo a 2 nd surgery on the ipsilateral breast due to positive SoC final margins following initial BCS prior to radiation or medical management # of patients in Arm 1	x100%	Patient-level early reoperation rate.
		P(2.16b) Arm 2 only = # of patients in Arm 2 that underwent or are scheduled to undergo a 2 nd surgery on the ipsilateral breast due to positive FGR final margins following initial BCS prior to radiation or medical management # of patients in Arm 2	x100%	

SBI-CIP 20-002 Rev: v1.8 A prospective multi-center clinical study evaluating the use of PD G 506 A and the Eagle V1.2 Imaging System for the visualization of carcinoma during breast conserving surgery Page: 38 of 157	·
--	---

Secondary Objectives	Parameter Description	Parameter Formula	Abbreviated Description
17. To characterize the impact	Sum of the weight (mg) of all tissue	P(2.17a) =	Amount of tissue removed
of FGR during BCS on the	removed based on SoC compared to the	Mean SoC tissue weight (mg) Arm 1 and Arm	with FGR beyond SoC.
amount of tissue removed	sum of the weight (mg) of all tissue	2:	
(Arm 1 and Arm 2).	removed based on FGR (patient-level	SoC tissue weight = Primary specimen (mg) +	
	analysis; Arm 1 and Arm 2).	SoC-driven cavity shave specimen(s) (mg)	
		P(2.17b) =	
		Mean FGR tissue weight (mg) Arm 2 only:	
		Total tissue weight = FL-driven cavity shave	
		specimen(s) (mg)	
18.To characterize the impact	Patient satisfaction with the cosmetic	P(2.18a) =	Patient satisfaction.
of FGR during BCS on the	outcome of breast conserving surgery	Mean Breast-Q Breast Conserving Therapy	
patient-reported cosmetic	performed based on SoC in	Module satisfaction with breasts score before	

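### Both P(2.15) numerators count any second ipsilateral operation within a year, although the endpoint is defined as surgery to remove suspected residual disease

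*Combined protocol and SAP*

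**What the plan says.** Section 7.2.2, objective 15, gives the endpoint in three ways.

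- **Description:** the percentage of patients having a second "surgery on the ipsilateral breast within 1 year of index BCS to remove" "suspected residual disease (patient-level analysis; Arm 1 and Arm 2". The sentence is split across two table fragments, but its sense is clear: the purpose of the operation is part of the endpoint.
- **Label:** "Patient-level re-operation rate due to suspected residual disease".
- **Formula:** the Arm 1 numerator is the number "of patients in Arm 1 that underwent a 2 nd surgery on the ipsilateral breast within 1 year of index BCS" and the Arm 2 numerator is the number "of patients in Arm 2 that underwent a 2 nd surgery on the ipsilateral breast within 1 year of index BCS". Neither mentions a reason; each stops at a second "surgery on the ipsilateral breast within 1 year of index BCS".

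The next endpoint, P(2.16), does carry its reason in the formula. Its Arm 2 numerator counts patients who had, or are scheduled for, a second "surgery on the ipsilateral breast due to positive FGR final margins following initial BCS prior to radiation or medical management".

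Section 15.5 refers to Section 7 for the detailed formulas. Section 15.7 compares re-operation rates between arms with Fisher's exact test. Section 8.1 lists re-excision within a year among the purposes of Arm 1.

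**The concern.** The words and the formula define different endpoints. A programmer who codes the formula counts every recorded second operation on the breast. A reader of the label takes the result as surgery for residual disease. Table splitting does not explain the gap, since both numerators are complete and both omit the reason.

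Re-operation is one of the few comparisons for which the control arm exists. Operations done for another reason add events that FGR is not meant to prevent, and if they are equally frequent in both arms they pull the rate ratio toward 1. There is also a timing issue. Under Section 8.1, the one-year data are analysed after the 3-month database lock and after all other endpoints, so an unresolved definition could end up being settled with those results known.

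**Working it through.** **1. Which operations can reach the numerator.** The formula can count only what is recorded.

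| Source | What is captured | Consequence for P(2.15) |
|---|---|---|
| Section 12.4.5 | All post-operative treatment started by the Week 2 visit; re-operation is named as an example; no restriction by purpose | An early re-operation for any reason can be recorded and counted |
| Sections 12.8, 12.9.1, 12.9.2 | At 3, 6 and 12 months, treatment directed at the primary cancer in the ipsilateral breast | Late cosmetic, symmetry or complication surgery is largely outside the data |
| Section 12.1, footnote q | Chart review for therapies related to the breast cancer diagnosis | Same filter |

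Cancer-directed surgery that was not for suspected residual disease still passes the later filters, for example surgery for recurrence or a mastectomy chosen on other grounds. No section asks for the reason for a second operation to be recorded for P(2.15), so such cases could not be reliably separated from the planned data.

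**2. Denominators.** The plan states no rate or power for P(2.15). The arm sizes come from P(1.1) (Section 15.2: null 1%, expected 3%, two-sided 0.05, 90% power):

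n = [(1.95996 × √(0.01 × 0.99) + 1.28155 × √(0.03 × 0.97)) / 0.02]² = 427.7, so 428 in Arm 2.

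Arm 1 is 428 / 6 = 71.3, so 72. Both match the plan.

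**3. Illustration of size.** Inputs:

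- Arm 1 residual-disease rate a = 23%, the Canadian one-year re-excision figure in Section 6.1.1.
- Arm 2 rate b = 11.5%, assumed (half of Arm 1).
- u, the share of the remaining patients with a second recorded operation for another reason, assumed 1% to 5% and equal in both arms.

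The literal formula then gives A = a + (1 − a)u and B = b + (1 − b)u. The difference becomes (a − b)(1 − u).

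Power uses 72 and 428 patients. The normal approximation is Φ[(A − B − 1.96 × SE₀) / SE₁], with SE₀ pooled and SE₁ unpooled. Fisher power sums the binomial probabilities of all tables with two-sided p ≤ 0.05; it was computed at u = 0 and 5% only.

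| u | Arm 1 | Arm 2 | Difference (points) | Ratio B/A | Power, normal | Power, Fisher |
|---|---|---|---|---|---|---|
| 0 | 23.0% | 11.5% | 11.5 | 0.50 | 72% | 69% |
| 1% | 23.8% | 12.4% | 11.4 | 0.52 | 70% | not run |
| 3% | 25.3% | 14.2% | 11.2 | 0.56 | 65% | not run |
| 5% | 26.9% | 15.9% | 10.9 | 0.59 | 60% | 56% |

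In patients, u = 1% adds 72 × 0.77 × 0.01 = 0.6 in Arm 1 and 428 × 0.885 × 0.01 = 3.8 in Arm 2. At u = 5% these become 2.8 and 18.9.

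With a smaller assumed effect, 23% versus 20%, Fisher power is only 8.6% at u = 0 and 7.5% at u = 5%, so the wording hardly matters to the test.

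**The case against.** The best defence is that the intent is plain. The description and label both give the reason, and Section 8.1 speaks of re-excision, which Section 5.1 defines as surgery done "because of positive margins found from the initial lumpectomy procedure". On this view the formula is shorthand. Section 15.5 is only a pointer and does not rank the formula above the description beside it, and Section 15.1 leaves further detail to the SAP. The endpoint is neither primary nor key secondary, it does not drive the sample size, and P(2.16) already supplies a re-operation comparison restricted by reason.

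Much of this stands: the low rank of the endpoint, the limited reach of Section 15.5, and above all the filter that follow-up capture imposes. Three things do not fall away:

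- The supporting sections do not agree on one meaning. Positive margins is a narrower criterion than suspected residual disease, so the text offers three readings: any second surgery, suspected residual disease, and positive margins.
- P(2.16) does not substitute for P(2.15). It covers early surgery before radiation or medical management and uses the margin criterion.
- Settling the intent does not make the endpoint computable while the reason for surgery is not required.

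A reader might go further and infer that complication, cosmetic and symmetry operations enter the rate freely and, because FGR removes extra tissue, differ by arm enough to hide or mimic an effect. The documents do not support that. Such surgery after Week 2 is largely not collected, and no section gives a rate for it in either arm or any basis for a difference between arms.

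**Conclusion.** The mismatch is certain: as written, the P(2.15) formula does not measure the endpoint it is labelled as. The consequence is confined to early re-operations recorded up to Week 2 for any reason and to later cancer-directed surgery done for a reason other than suspected residual disease.

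The size is unknown because the documents give no frequency for either. Under the assumptions above, the rate ratio moves from 0.50 to between 0.52 and 0.59, while the absolute difference moves by at most about 0.6 points. Power falls by about 2 points (normal approximation, u = 1%) to about 13 points (Fisher, u = 5%). The upper end depends wholly on the assumed 5%. This concerns one non-key secondary comparison and leaves the primary and key secondary results untouched.

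**What to change.** - Add the restriction to surgery for removal of suspected residual disease to both P(2.15) numerators, so that they match the endpoint's own description. The P(2.16) wording should not be copied, because its margin criterion is different.
- Add one eCRF field giving the reason for each second ipsilateral operation, completed in the same way in both arms. If follow-up has begun, fill it from the chart for operations already entered.
- Report other second ipsilateral operations by arm only as far as they are captured, and say that the list is incomplete, since follow-up after Week 2 is limited to treatment of the primary cancer.
- Make the change before the 3-month database lock.

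The cost is a wording change plus one eCRF field. Sample size and the test are unaffected.
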